2.4.4.1.2 Subgroup analyses

Where appropriate for the size of a subgroup, exploratory analyses are performed on the primary endpoint to summarize the treatment effects across subgroups.

For each subgroup, the primary efficacy variable will be analyzed in the ITT population using post-baseline HbA1c data available on the 24-week on treatment period, (to assess the on-treatment estimand). A similar MMRM approach as described for primary analysis will be applied adding the corresponding subgroup factor, subgroup factor-by-treatment interaction, subgroup factor-by-visit interaction and subgroup factor-by-visit-by treatment interaction.

The subgroups will be defined by the following baseline and screening factors:

- Age group (<65 and \geq 65 years of age),
- Gender (male, female),
- Baseline BMI (<30; ≥ 30 and <35; ≥ 35 kg/m²),
- Randomization stratum of screening HbA1c (< 8.0%, $\geq 8.0\%$),
- Randomization stratum of use of SU or meglitinides at screening (yes, no),
- Number of previous non-insulin anti-hyperglycemic agent (0, 1, 2, >2),
- Previous non-insulin anti-hyperglycemic treatment at screening: GLP-1RA (yes/no),
- Previous non-insulin anti-hyperglycemic treatment at screening: DPP-4 inhibitor (yes/no),
- Previous non-insulin anti-hyperglycemic treatment at screening: SGLT-2 inhibitor (yes/no),
- Duration of diabetes ($<10, \ge 10$ years),
- Baseline estimated GFR categories (mL/min/1.73m²): (<15; [15-30[; [30-60[; [60-90[; ≥90).

If the subgroup factor is a randomization stratification factor, then the strata as per IVRS will be used.

The randomization strata of screening HbA1c and use of SU or meglitinides at screening will not be included in the model.

Least Square Means Difference versus Tresiba at Week 24 will be provided, as well as the corresponding SEs and 95% CI, within each subgroup. The significance level of the treatment-by-subgroup factor interaction term at Week 24 will also be provided for each factor for descriptive purpose. Forest plots will be provided.

Subgroups analyses using randomization strata derived as per electronic case report form (e-CRF), should be performed only if necessary (in case of high number of discrepancies between stratum as per IRT and stratum as per e-CRF) and should be considered as sensitivity analysis.

Further subgroup analyses may be performed if deemed necessary for interpretation of results.

2.4.4.1.3 Key sensitivity analysis

A first sensitivity analysis will be conducted in the ITT population, using all available postbaseline HbA1c values, regardless of study treatment discontinuation and rescue therapy initiation (analysis on the 24-week randomized period, to assess the ITT estimand). The same MMRM model as described for primary analysis will be used.

A second sensitivity analysis will be performed on the change in HbA1c from baseline to Week 24 in the Per-protocol population (analysis on 24-week on treatment period, to assess the on-treatment estimand). The same MMRM model as described for primary analysis will be used.

2.4.4.1.4 Sensitivity analyses to handle missing data

Sensitivity analyses will be conducted to assess the robustness of primary efficacy analysis with regard to missing data.(5).

Description of missing data

Missing data in the primary efficacy analysis (analysis on 24-week on treatment period, to assess the on-treatment estimand).

The following analyses will be performed on the ITT population to explore the missing data frequency and pattern in the primary efficacy analysis:

In order to explore missing data patterns for HbA1c in the primary efficacy analysis, number and percentage of patients in each of the following categories will be presented by treatment group:

- Pattern 1: patients without baseline if any,
- Pattern 2: patients with baseline but without post-baseline value during the 24-week ontreatment period,
- Pattern 3: patients with baseline and at least one post-baseline value during the 24-week on treatment period but not at Week 24,
- Pattern 4: patients with baseline and Week 24 value during the 24-week on-treatment Period.

Missing data in the key sensitivity efficacy analysis

The following analyses will be performed on the ITT population to explore the missing data frequency and pattern in the key sensitivity analysis:

In order to explore missing data patterns for HbA1c in the key sensitivity analysis, number and percentage of patients in each of the following categories will be presented by treatment group:

- Pattern 1: patients without baseline if any (ITT estimand),
- Pattern 2: patients with baseline but without post-baseline value (ITT estimand),
- Pattern 3: patients with baseline and at least one post-baseline value but not at Week 24 (ITT estimand),
- Pattern 4: patients with baseline and Week 24 value (ITT estimand).

Penalized multiple imputation

In order to assess the impact of missing data, the change in HbA1c from baseline to Week 24 in % using HbA1c values during the randomized 24-week period, to assess the ITT estimand (all post baseline available data), will be analyzed in the ITT population using a multiple imputation approach to account for missing data at any time points (including missing baseline, Week 8, Week 12 and Week 24) followed by the testing of treatment arms using an analysis of covariance (ANCOVA) model.

Missing data will be imputed 100 times to generate 100 complete data sets with the MI SAS procedure. For each simulation leading to negative imputed value, another value will be redrawn for imputation using MINIMUM option of MI SAS procedure. Since in general, the missing pattern will not be monotone, a two-step approach will be used:

- Step 1: the markov chain Monte Carlo (MCMC) method will be used in conjunction with the IMPUTE=MONOTONE option to create an imputed data set with a monotone missing pattern,
- Step 2: using the monotone data set from Step 1, missing data will be imputed using the regression method.

The imputation model for Step 1 will include the treatment group, baseline HbA1c value, as well as HbA1c values at Week 8, Week 12, and Week 24.

The imputation model for Step 2 will includes the same variables as in Step 1 with the randomization strata.

The imputed HbA1c value at Week 24 in the Toujeo group will then be penalized by adding 0.3% (corresponding to the non-inferiority margin) to the imputed HbA1c value whereas the imputed HbA1c in the Tresiba group will not be penalized. The change in HbA1c from baseline to endpoint will then be derived from observed and imputed (penalized or not) HbA1c value at Week 24.

The 100 complete data sets will then be analyzed using an analysis of covariance (ANCOVA) model including the fixed categorical effects and randomization stratum of use of SU or meglitinides at screening (Yes, No), treatment group (Toujeo, Tresiba), as well as, the continuous fixed covariate of baseline HbA1c value. The MIANALYZE procedure will then be used to generate valid statistical inferences by combining results from the 100 analyses using Rubin's formulae.

This procedure will provide baseline adjusted least-squares means estimates at Week 24 for both treatment groups, as well as, the differences of these estimates, with their corresponding SEs and 95% CIs.

Tipping point analysis

Robustness of the primary analysis results to departure from the MAR assumption will be explored in the ITT population using tipping-point analysis based on the pattern mixture model approach.

The considered pattern mixture model will introduce a sensitivity parameter, δ , corresponding to the difference in means between patients with missing data and patients with observed data.

Estimations will be performed using the same multiple imputation approach as described above. δ will be added to the imputed values ($\delta = 0$ corresponds to the missing at random [MAR]

assumption). For each assessed value of δ by treatment group will correspond an estimated mean HbA1c reduction per group and an estimated treatment effect.

To investigate how the conclusions depend on the adopted values of δ , the testing will be repeated over a range of plausible values for the pairs (δ Toujeo, δ Tresiba). Results will be then summarized using graphs.

Further pattern mixture models could be explored depending on the observed missing data pattern in the Toujeo arm.

2.4.4.1.5 Sensitivity to randomization strata

In order to assess the robustness of the primary analysis to randomization stratum errors, ie, the stratum recorded in IVRS differs from the actual one), the MMRM model will be re-run including the actual stratum as per the e-CRF instead of the stratum recorded in IVRS.

2.4.4.2 Analyses of secondary efficacy endpoints

2.4.4.2.1 Analyses of secondary efficacy endpoints

Secondary efficacy endpoints are described in Section 2.1.3.2.

All secondary efficacy endpoints will be analyzed or summarized on the 24-week on treatment period (to assess the on-treatment estimand) using the ITT population.

The following secondary efficacy endpoint will be analyzed using the same model (same analysis) as the one used for primary endpoint (MMRM model) as described in Section 2.4.4.1.1.

• HbA1c (%): change from baseline to Week 12;

The following secondary efficacy endpoints will be analyzed using the same approach as the one used for primary endpoint (MMRM model) as described in Section 2.4.4.1.1. The model will include fixed categorical effects of treatment group, visit, treatment-by-visit interaction, randomization stratum of use of SU or meglitinides at screening (Yes, No), randomization stratum of HbA1c (< 8.0 % and \geq 8.0%), the continuous fixed covariates of the corresponding baseline value, and baseline value-by-visit interaction.

For the model on change FPG, the visit term has 3 levels (Week 8, Week 12 and Week 24).

For the models on Fasting SMPG data, the visit term has 7 levels (Week 2, Week 4, Week 8, Week 12, Week 16, Week 20 and Week 24).

For the models on 8-point SMPG data, the visit term has 7 levels (Week 12 and Week 24).

- FPG: change from baseline to Week 12 and Week 24;
- Fasting SMPG: change from baseline to Week 12 and Week 24;

- Change of mean 24-hour plasma glucose based on 8-point SMPG from baseline to Week 12 and Week 24;
- Change in variability of fasting SMPG from baseline to Week 12 and Week 24;
- Change in variability of 24-hour plasma glucose based on 8-point SMPG from baseline to Week 12 and Week 24.

The following secondary endpoints will be analyzed using descriptive measures as described in Section 2.4.4.1.1:

- Change in 8-point SMPG profiles per time-point from baseline to Week 12 and Week 24;
- Change in 4-point SMPG profiles per time-point from baseline to Week 4, Week 8, Week 12 and Week 24.

Basal insulin dose (U and U/kg body weight): change from baseline to Week 12 and Week 24 (see Section 2.4.3.1);

The following secondary endpoints will be analyzed using logistic regression model adjusted on randomization strata of screening HbA1c (<8.0%, $\geq8.0\%$) and randomization strata of SU or meglitinides at screening (yes/no). This model will also estimate the Odds Ratio of Toujeo and Tresiba and its corresponding 95% CI.

- Percentage (%) of patients reaching target HbA1c <7% and ≤6.5% at Week 12 and Week 24,
- Percentage (%) of patients reaching target HbA1c <7% at Week 24 without severe and/or confirmed hypoglycemia (≤70 mg/dL) during the 24 weeks treatment period,
- Percentage (%) of patients reaching target HbA1c <7% at Week 24 without severe and/or confirmed hypoglycemia (<54 mg/dL) during the 24 weeks treatment period,
- Percentage (%) of patients reaching target HbA1c <7% at Week 12 without severe and/or confirmed hypoglycemia (≤70 mg/dL) during the 12 weeks treatment period,
- Percentage (%) of patients reaching target HbA1c <7% at Week 12 without severe and/or confirmed hypoglycemia (<54 mg/dL) during the 12 weeks treatment period,
- Percentage (%) of patients reaching target HbA1c ≤6.5% at Week 24 without severe and/or confirmed hypoglycemia (≤70 mg/dL) during the 24 weeks treatment period,
- Percentage (%) of patients reaching target HbA1c ≤6.5% at Week 24 without severe and/or confirmed hypoglycemia (<54 mg/dL) during the 24 weeks treatment period,
- Percentage (%) of patients reaching target HbA1c ≤6.5% at Week 12 without severe and/or confirmed hypoglycemia (≤70 mg/dL) during the 12 weeks treatment period,
- Percentage (%) of patients reaching target HbA1c ≤6.5% at Week 12 without severe and/or confirmed hypoglycemia (<54 mg/dL) during the 12 weeks treatment period,
- Percentage (%) of patients with SU or meglitinide dose reduction due to hypoglycemia,

• Percentage of patients requiring rescue therapy during 24 weeks treatment period.

Hypoglycemia will be determined during the 12-week on-treatment period and the 24-week on treatment period, respectively (used for efficacy endpoint, as defined in Section 2.1.3).

Patients who initiate rescue therapy during the 12-week on-treatment period or during the 24-week on treatment period, respectively, will be considered as failure for this given period.

Patients with missing HbA1c at a given visit will be considered as failure (non-responders) for this given visit.

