#### 8.5 METHOD OF ASSIGNING PATIENTS TO TREATMENT GROUP

The Trial Supply Operations Manager provides the treatment kit number list and the Study Biostatistician provides the randomization scheme to the interactive voice response system (IVRS)/interactive web response system (IWRS). Then, the IVRS/IWRS generates the patient randomization list according to which it allocates treatment arms to the patients.

The study medications are provided in open-label boxes and each type of kit is identified with a treatment number.

At the screening visit the investigator or designee contacts the IVRS/IWRS center to receive the patient number. The patient number is composed of 9-digit number containing the 3-digit country code, the 3-digit center code and the 3-digit patient chronological number (which is 001 for the first patient screened in a center, 002 for the second patient screened in the same center etc).

Patients are randomized to receive during the 24 weeks comparative efficacy and safety period, either Toujeo or Tresiba. The randomization ratio is 1:1. The randomization is stratified by screening HbA1c value (<8%,  $\geq8\%$ ) and SU or meglitinides use before the day of screening (Yes; No).

The treatment kits are allocated using a centralized treatment allocation system (IVRS/IWRS). On V2 (D1), after assessment results are reviewed and baseline assessment is completed, IVRS/IWRS is contacted for randomization and the first treatment kit(s) allocation. The investigator or designee has to call the IVRS/IWRS to provide some information (such as patient number provided by IVRS/IWRS at screening visit, date of birth, etc). Afterwards the IVRS/IWRS is contacted again each time a new treatment kit(s) allocation is necessary, ie, at Weeks 4, 8, 12, 16 and 20. The IVRS/IWRS will allocate treatment kit(s) using their treatment number.

A randomized patient is defined as a patient who is registered and assigned with a randomized treatment arm from the IVRS/IWRS, as documented from IVRS/IWRS log file, regardless whether the treatment kit was used or not.

A patient cannot be randomized more than once to the study.

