#### 9.1.1 Primary endpoint

• Change in HbA1c from baseline to Week 24.

For the eligibility and efficacy assessments of the study, HbA1c is measured by a certified level I "National Glycohemoglobin Standardization Program" (NGSP) central laboratory.

HbA1c is assayed at screening (Visit 1, Week -2); at baseline (Visit 2; Day 1); at Visit 10 (Week 8); Visit 14 (Week 12); and Visit 20 (Week 24; final primary endpoint assessment visit).

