# 11.4.2.2 Analyses of secondary efficacy endpoints

Secondary efficacy endpoints are described in Section 9.2

All secondary efficacy endpoints will be analyzed or summarized on the 24-week on treatment period using the ITT population.

The following secondary efficacy endpoint will be analyzed using the same approach as the one used for primary endpoint (MMRM model) as described in Section 11.4.2.1.

• HbA1c (%): change from baseline to Week 12;

The following secondary efficacy endpoints will be analyzed using the same approach as the one used for primary endpoint (MMRM model) as described in Section 11.4.2.1 The model will include fixed categorical effects of treatment group, visit, treatment-by-visit interaction, randomization stratum of use of SU or meglitinides at screening (Yes, No), randomization stratum of HbA1c (< 8.0 % and  $\geq$  8.0%), the continuous fixed covariates of the corresponding baseline value, and baseline value-by-visit interaction.

- FPG: change from baseline to Week 12 and Week 24;
- Fasting SMPG: change from baseline to Week 12 and Week 24;
- Change in 8-point SMPG profiles per time-point from baseline to Week 12 and Week 24;
- Change in 4-point SMPG profiles per time-point from baseline to Week 12 and Week 24;
- Change of mean 24-hour plasma glucose based on 8-point SMPG from baseline to Week 12 and Week 24;
- Change in variability of fasting SMPG and 24-hour plasma glucose based on 8-point SMPG from baseline to Week 12 and Week 24;
- Basal insulin dose(U and U/kg body weight): change from baseline to Week 12 and Week 24;

The following secondary endpoints will be analyzed using logistic regression model adjusted on randomization strata of screening HbA1c (<8.0%,  $\geq8.0\%$ ) and randomization strata of SU used at screening (yes/no). This model will also estimate the Odds Ratio of Toujeo and Tresiba and its corresponding 95% CI.

Percentage (%) of patients reaching target HbA1c <7% and ≤ 6.5% at Week 12 and Week 24;

- Percentage (%) of patients reaching target HbA1c <7% and ≤ 6.5% at Week 12 and Week 24 without severe and/or confirmed hypoglycemia (70 mg/dL and 54 mg/dL as cut off point) event during the 12 weeks treatment period and the 24 weeks treatment period;
- Percentage (%) of patients with SU or meglitinide dose reduction due to hypoglycemia;
- Percentage of patients requiring rescue therapy during 24 weeks treatment period

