2.4.4.1 Analysis of primary efficacy endpoint(s)

2.4.4.1.1 Primary efficacy analysis

The primary efficacy variable, change in HbA1c from baseline to Week 24 in % as defined in Section 2.1.3.1 will be analyzed in the ITT population using available data during the 24-week on treatment period (defined in Section 2.1.4, used to assess the on-treatment estimand). A mixed-effect model with repeated measures (MMRM) approach will be used, under the missing at random framework carried out via SAS PROC MIXED using an adequate contrast at Visit 20 (Week 24).

The model will include fixed categorical effects of treatment group (Toujeo, Tresiba), visit (Week 8, Week 12, Week 24), treatment-by-visit interaction, randomization stratum of use of SU or meglitinides at screening (Yes, No) as well as, the continuous fixed covariates of baseline HbA1c value and baseline HbA1c value-by-visit interaction.

This model will be run with an unstructured correlation matrix to model the within-patient errors.

Parameters will be estimated using restricted maximum likelihood method with the Newton-Raphson algorithm. Denominator degrees of freedom will be estimated using Satterthwaite's approximation.

This model will provide baseline adjusted least squares (LS) means estimates at Week 24 for both treatment groups, as well as, the differences of these estimates, with their corresponding standard error (SEs) and 95% CIs.

This analysis will be performed using the randomization strata as per IVRS.

A stepwise closed testing approach will be used for the primary efficacy variable to assess noninferiority and superiority sequentially detailed in Section 2.4.4.3:

- Step 1 will proceed to assess non-inferiority Toujeo versus Tresiba. To assess noninferiority, the upper bound of the two-sided 95% CI for the difference in the mean change in HbA1c from baseline to Week 24 between Toujeo and Tresiba will be compared with the predefined non-inferiority margin of 0.3% HbA1c. Non-inferiority will be demonstrated if the upper bound of the two-sided 95% CI of the difference between Toujeo and Tresiba on ITT population is <0.3%.
- Step 2 will test superiority of Toujeo over Tresiba, only if non-inferiority of Toujeo versus Tresiba has been demonstrated. The superiority of Toujeo over Tresiba will be demonstrated if the upper bound of the two-sided 95% CI for the difference in the mean change in HbA1c from baseline to Week 24 between Toujeo over Tresiba on ITT population is <0 (zero).

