2.4.4.4 Multiplicity issues

To control the type I error, a hierarchical step-down testing procedure described by Hochberg and Tamhane will be applied for the primary efficacy endpoint to assess non-inferiority and superiority sequentially (see Section 2.4.4.1).

- Step 1: non-inferiority comparison of the mean change from baseline to Week 24 in HbA1c with Toujeo compared to Tresiba.
- Step 2: only if non-inferiority of Toujeo relative to Tresiba in step 1 is demonstrated, superiority of Toujeo over Tresiba in changes in HbA1c from baseline to Week 24 will be assessed.

No multiplicity adjustment will be made on secondary efficacy variables; 95% confidence intervals (95% CI) and P-values presented for these endpoints will be done for descriptive purpose only.

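### The logistic models for the twelve HbA1c-target and composite endpoints carry HbA1c only as a two-level screening stratum and leave out the continuous baseline value, giving up a little test efficiency

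*SAP*

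**What the plan says.** SAP 2.4.4.2.1 introduces the responder analyses with "The following secondary endpoints will be analyzed using logistic regression model adjusted on randomization strata of screening HbA1c", split at 8.0%. It adds "randomization strata of SU or meglitinides at screening (yes/no") as the second term. On the effect measure it says "This model will also estimate the Odds Ratio of Toujeo and Tresiba and its corresponding 95% CI". Protocol 11.4.2.2 has the same plan, opening "The following secondary endpoints will be analyzed using logistic regression model adjusted on" the randomization strata.

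The list covers four target endpoints (two HbA1c thresholds at two visits) and eight composites (the same four, each with two hypoglycemia cut-offs). SU/meglitinide dose reduction and rescue therapy are on the same list.

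The two adjustment terms are the stratification factors of Protocol 8.5 ("The randomization is stratified by screening" HbA1c and by SU/meglitinide use). Protocol 9.1.1 shows that a separate baseline assay exists: "HbA1c is assayed at screening (Visit 1, Week -2); at baseline (Visit 2; Day 1"). The primary model in SAP 2.4.4.1.1 includes "the continuous fixed covariates of baseline HbA1c value and baseline HbA1c value-by-visit interaction". On inferential status, SAP 2.4.4.4 says "P-values presented for these endpoints will be done for descriptive purpose only".

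**The concern.** Eligible screening HbA1c runs from 7.5% to 10.5% (Protocol 7.2.1, E 01). The chance of ending below 7% or at 6.5% should depend on the starting value, yet the upper stratum treats a patient at 8.0% and one at 10.5% alike. The stratum also uses the screening value, so the Day 1 baseline does not enter these models.

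Elsewhere the SAP uses a continuous baseline. The HbA1c MMRM and the multiple-imputation ANCOVA use continuous baseline HbA1c. The FPG, fasting SMPG and 24-hour glucose MMRMs use both strata plus their own continuous baseline value. The DTSQc ANCOVA uses both strata plus the baseline DTSQs score. No reason is given for treating the HbA1c-target models differently.

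At stake are some efficiency in twelve reported comparisons and some protection against chance imbalance in starting HbA1c within the upper stratum. Protocol 9.5 relies on the responder analyses to support the clinical relevance of the HbA1c reduction.

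**Working it through.** **The plan's own figure.** The documents give no power, standard error or responder rate for these endpoints. The only stated calculation is for the primary endpoint (margin 0.3, SD 1.4, true difference 0, one-sided 0.025, power 90%):

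n per arm = 2 × (1.960 + 1.282)² × 1.4² / 0.3² ≈ 458, against the stated 460. Power at 460 per arm is 90.1%. The figure reproduces, and this point does not affect it.

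**Responder model: inputs.**
- From the documents: 920 patients, 1:1 allocation, screening HbA1c 7.5% to 10.5%, stratum cut at 8.0%, an SU/meglitinide stratum, target <7%.
- Assumed: screening HbA1c normal (mean 8.7, SD 0.9) truncated to the eligible range; baseline = screening + error of SD 0.3; control mean at Week 24 about 7.1; slope of Week 24 on baseline HbA1c 0.2 to 0.6; residual SD 0.8 to 1.3; treatment shift 0.2 residual SD in favour of Toujeo; SU use 60%.

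Each scenario has 1,500 simulated trials. Each trial is fitted with the planned model (two strata) and with the same model plus continuous baseline HbA1c. Efficiency gain = [(log OR/SE with baseline) / (log OR/SE planned)]² − 1. Power is two-sided at 5%. The last column is the variance of a standardised risk difference, planned divided by with baseline.

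| Slope | Resid. SD | Log OR | SE of log OR | Efficiency gain | Power (%) | RD variance ratio |
|---|---|---|---|---|---|---|
| 0.2 | 0.8 | 0.3141 → 0.3196 | 0.1333 → 0.1346 | 1.7% | 64.6 → 66.1 | 1.014 |
| 0.2 | 1.0 | 0.3137 → 0.3172 | 0.1331 → 0.1339 | 1.0% | 65.1 → 65.5 | 1.004 |
| 0.2 | 1.3 | 0.3158 → 0.3180 | 0.1329 → 0.1335 | 0.5% | 66.7 → 66.4 | 1.004 |
| 0.4 | 0.8 | 0.3154 → 0.3343 | 0.1347 → 0.1391 | 5.3% | 66.7 → 69.3 | 1.049 |
| 0.4 | 1.0 | 0.3122 → 0.3247 | 0.1340 → 0.1369 | 3.6% | 65.1 → 66.4 | 1.016 |
| 0.4 | 1.3 | 0.3142 → 0.3223 | 0.1334 → 0.1352 | 2.4% | 64.9 → 66.2 | 1.031 |
| 0.6 | 0.8 | 0.2936 → 0.3340 | 0.1367 → 0.1460 | 13.5% | 56.5 → 63.0 | 1.140 |
| 0.6 | 1.0 | 0.3005 → 0.3264 | 0.1353 → 0.1415 | 7.8% | 61.3 → 64.5 | 1.075 |
| 0.6 | 1.3 | 0.3066 → 0.3254 | 0.1343 → 0.1381 | 6.5% | 62.8 → 66.6 | 1.067 |

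Strongest scenario worked through: planned z = 0.2936/0.1367 = 2.148; with baseline 0.3340/0.1460 = 2.288; (2.288/2.148)² = 1.135. The SE rises by 0.1460/0.1367 − 1 = 6.8%, and the log OR rises by 0.3340/0.2936 − 1 = 13.8%. The gain therefore comes from the conditional odds ratio moving away from 1 by more than its SE grows.

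The Monte Carlo error of one power figure is about √(0.65 × 0.35 / 1,500) = 1.2 points. The small drop in the third row is no evidence of a loss.

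**Second set, including the 6.5% target.** With slope 0.3 to 0.5, residual SD 0.8 to 1.0, a treatment shift of 0.2% HbA1c and 600 trials per scenario, efficiency rose 1.4% to 9.7% and power 0.2 to 4.8 points.

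**Chance imbalance.** In that set the planned log OR correlated −0.12 to −0.29 with the treatment difference in baseline HbA1c inside the ≥8.0% stratum. With continuous baseline added, the correlation was at most 0.06 in absolute value. An imbalance of 0.1 HbA1c points, about 2 SD of what randomization produces, moved the planned log OR by 0.03 to 0.08. Against an SE of 0.13 to 0.15, that is between 0.03/0.15 = 0.20 and 0.08/0.13 = 0.62 of one SE.

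**The case against.** The strongest objection concerns precision. A reader might infer that the planned model wastes precision, so that the reported intervals are wider than they need be. The documents do not support that, because the planned measure is an odds ratio and the SE of its logarithm rose in every scenario when baseline was added. Only a standardised risk difference, which is not the planned measure for these endpoints, would be estimated more precisely. This part of the objection stands in full.

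A reader might also infer that HbA1c stratum is the only adjustment, or that the model is wrong. Neither holds. The SU/meglitinide stratum is also in the model, the two terms are exactly the stratification factors, and both documents prespecify them. Nor do all the SAP's continuous models use continuous baseline HbA1c: the FPG and SMPG models use the HbA1c stratum plus their own baseline.

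The objection is also right that the consequences are limited. These endpoints have no power target and sit outside the type I error procedure. Chance imbalance is ordinary sampling variation that the interval covers. The HbA1c effect itself is adjusted for continuous baseline in the MMRM at Weeks 12 and 24. The sizes depend on assumed inputs, and the composites, which also require freedom from hypoglycemia, were not simulated.

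What remains is that a prognostic value already in the database is left out of the models where it bears directly on the outcome. Every simulated scenario showed an efficiency gain from adding it.

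**Conclusion.** The point holds as an optional improvement. The twelve models are valid as planned, and no confirmatory conclusion depends on them. For the <7% target they give up about 0.5% to 13.5% in test efficiency, equivalent to roughly 5 to 124 of 920 patients (0.005 × 920 and 0.135 × 920), or about 0 to 6 power points. The upper end needs a strong dependence of Week 24 on baseline HbA1c (slope 0.6, residual SD 0.8); most scenarios lie well below it. The models are also somewhat more exposed to chance baseline imbalance within the ≥8.0% stratum, though the effect is a fraction of one standard error.

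The distribution of HbA1c, the slope, the residual SD, the treatment shift and the SU share are assumptions; the documents give neither a responder rate nor a baseline-to-Week-24 correlation. The size for the composites is not established.

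**What to change.** In SAP 2.4.4.2.1, add continuous baseline HbA1c to the logistic models for the four HbA1c-target and eight composite endpoints, keep both randomization strata, and state that the odds ratio is conditional on baseline HbA1c as well as the strata. If the main model is to stay as it is, prespecify the extended model as a sensitivity analysis before database lock.

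Two details need a sentence each:
- **Scope.** SAP 2.4.5.1 says the hypoglycemia logistic models follow the approach for the categorical efficacy endpoints. State that they, and the rescue and SU/meglitinide dose-reduction models, keep the two strata only, so that the new term is not carried over by reference.
- **Missing baseline.** SAP 2.5.2 counts a patient without baseline HbA1c as not reaching target, but a missing covariate would drop that patient from the model. Baseline is the last value before first injection (SAP 2.1.3) and screening HbA1c is needed for eligibility, so the screening value can serve; say so.

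The cost is one covariate and a few lines of text, with no new data. The drawback is that the odds ratio becomes more conditional and its standard error rises slightly, by up to about 7% in the scenarios above.
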